6.5 SUBJECT, STUDY AND SITE DISCONTINUATION

6.5.1 Subject Withdrawal

Patients have the right at any time and for any reason to withdraw their consent that their data are collected and used for the study. Reasons for withdrawal from the study may include, but are not limited to, the following:

- Patient withdrawal of consent at any time;
- Any medical condition that the investigator determines may jeopardize the patient's safety
 if he/she continues in the study;

- Investigator determines it is in the best interest of the patient;
- Patient's inability or unwillingness to comply with protocol requirements or noncompliance despite appropriate education measures taken by the clinical site.
- Patient died.
- Patient lost to follow-up.

Patients may elect to withdraw from the physical activity monitoring but continue participation in the remainder of the study. If a patient decides to withdraw only from the physical activity monitoring prematurely, the patient will continue with the follow-up visits as per the study protocol. Every effort should be made to obtain information on subjects who withdraw from the study. The primary reason for withdrawal from the study should be documented on the appropriate CRF page. Subjects will not be followed for any reason after consent has been withdrawn. Patients who withdraw from this part of the study will not be replaced.

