## 2.2 OUTCOME MEASURES

The co-primary outcome measures are given by the physical activity data collected through a wearable device (i.e., fitness tracker) in terms of active minute, METs and steps count.

According to the protocol (see Study protocol, Section 6.1.1), a valid day of monitoring is defined as at least 10 wearing hours per day. Only data from days in which the fitness tracker was worn for at least 10 hours will be included in the statistical analysis (see Appendix 3 for the derivation of the wearing time).

The minutes are saved in two different sets of data collected by the fitness tracker. For each set, minutes are categorized by intensity of the activity done.

The first set is comprised of the minutes categorized accordingly to the time collected in each heart zones (following referred as “heart zone minutes”):

- fat-burn minutes,
- cardio minutes,
- peak minutes.

The second set is comprised of the minutes categorized accordingly to the active zones (following referred as “active zone minutes”):

- lightly active minutes,
- fairly active minutes,
- very active minutes.

The conversion from heart zones to active zones is not shared by the owner of the fitness tracker but it is known that it is based on the METs (Metabolic Equivalent of Task). The MET is the objective measure of the ratio of the rate at which a person expends energy, relative to the mass of that person, while performing some specific physical activity compared to a reference. METs calculated by the fitness tracker are not directly available but must be derived.

In our analysis, the METs will be derived by using the following formula:

$$1 \text{ MET} = \frac{\text{kcal}}{\text{kg} * \text{h}}$$

where:

- $kcal$  will be given by the sum of calories collected by the fitness tracker during the time spent in fat-burn, cardio and peak heart zones, respectively.
- $kg$  will be given by the weight collected in the eCRF at baseline and every 3 months when the observation visit is conducted and the weigh is collected (the weight is assumed constant between each visit and the subsequent, in case of missing assessment, the last available value will be carried forward).
- $h$  is the time that will be derived as sum of fat-burn minutes, cardio minutes, and peak minutes.

The minutes will be also analyzed in terms of overall sum:

$$\begin{aligned} \text{overall heart zone minutes} &= \\ &= \text{fatburn minutes} + \text{cardio minutes} + \text{peak minutes} \end{aligned}$$

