#### **4.1.2 Evaluable population**

The evaluable population will consist of all enrolled patients with at least 6 valid months of physical activity evaluations during the study.

The patients with 6 valid months of physical activity will be defined by the presence of the two following conditions:

- an Extent of Exposure to the fitness tracker of at least 6 months (180 days) (see Section 4.3.1 for the definition of Exposure).

AND

- a compliance to the use of the fitness tracker of at least 50% in the period defined by the extent of exposure (see Section 4.3.2.1 for the definition of the compliance respect to the exposure).

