#### **4.1.3 Intention-to-treat Population (ITT)**

The Intention-To-Treat Population will consist of all enrolled patients who received the ePRO application and the fitness tracker.

All objectives will be evaluated both on the Evaluable population and on the ITT population. In case that the Evaluable population will consist of less the 50% (< 50%) of the ENR populations, only the primary endpoint and the secondary endpoint on the type of physical activity will be assessed on the Evaluable populations while all endpoints will be assessed on the ITT population.

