## **4.4 EFFICACY ANALYSIS**

#### **4.4.1 Co-primary Endpoints**

All the co-primary endpoints presented in Section 2.2.1, i.e.:

- active minutes:
  - heart zone minutes (overall, fat-burn minutes, cardio minutes, peak minutes)
  - active zone minutes (overall, lightly active minutes, fairly active minutes, very active minutes)
  - MVPA minutes
- METs
- number of steps

will be summarized at subject level as median per day (i.e. the median of each parameter will be calculated by using all the valid days collected during the observational period for each subject). Each parameter, derived as median per day at subject level, will be analyzed by means of descriptive statistics as described in Section 4. The 95% confidence interval for the mean will be also displayed.

The statistics will be shown overall and by age groups (12-17, 18-30 and 31-50). The comparison among the age groups will be performed by means of a one-way ANOVA or, if assumptions of normality is not confirmed (by a visual inspection: histogram and qq-plot), by means of a Kruskal-Wallis test.

Daily physical activity will also be summarized:

- by start of any newly approved drug for haemophilia (see Section 4.4.4 for subgroup definition).
- by COVID-19 period on the EVL population (see Section 4.4.4 for subgroup definition).
- by month through the entire observational period on the EVL to observe the impact of COVID-19.

Data will be summarized at subject level considering data collected in each period above-mentioned.

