### **Number of patients who are adherent to WHO Guidelines for the definition of physical activity**

Number and proportion along with the 95%CI (Clopper-Pearson's formula) of subjects who are adherent to World Health Organization Guidelines for the definition of physical activity will be calculated in the whole sample and compared by age group.

Adherence to WHO guidelines will also be summarized:

- by start of any newly approved drug for haemophilia (see Section 4.4.4 for subgroup definition).
- by COVID-19 period on the EVL population (see Section 4.4.4 for subgroup definition).
- by month through the entire observational period on the EVL to observe the impact of COVID-19.

The adherence will be summarized considering data collected in each period above-mentioned.

Other subgroup analyzes: severity of the disease (see Section 4.4.4 for subgroup definition).

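### The SAP specifies the lockdown-period and by-month tables of tracker activity and WHO adherence on the Evaluable set only, so some patients with valid data in a period are left out because of later or overall wear; an ITT companion should be specified

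*SAP*

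**What the plan says.** **Which set the tables use.** SAP 4.4.1 lists daily activity "by COVID-19 period on the EVL population (see Section 4.4.4 for subgroup definition") and, in the next line, by month on the EVL. SAP 4.4.2 repeats both lines for activity by type and for WHO adherence, the latter "by month through the entire observational period on the EVL to observe the impact of COVID-19". EVL is not formally defined, but the Evaluable population is the only plausible reading.

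**Who is Evaluable.** SAP 4.1.2 requires "an Extent of Exposure to the fitness tracker of at least 6 months (180 days") together with "a compliance to the use of the fitness tracker of at least 50% in the period defined by the extent of exposure". SAP 4.3.1 counts exposure from the first to the last valid day.

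**General rule on sets.** SAP 4.1.3 says: "All objectives will be evaluated both on the Evaluable population and on the ITT population". It adds that if Evaluable is under half of Enrolled, only the primary endpoint and the activity-type endpoint are still assessed on Evaluable, while everything is assessed on ITT. Protocol 6.7 names only the Evaluable population for primary, secondary and exploratory variables.

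**Data filter and content.** SAP 2.2: "Only data from days in which the fitness tracker was worn for at least 10 hours will be included in the statistical analysis". SAP 4.4.1, on the period tables: "Data will be summarized at subject level considering data collected in each period above-mentioned".

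**Withdrawal from tracking.** Protocol 6.5.1: "Patients may elect to withdraw from the physical activity monitoring but continue participation in the remainder of the study".

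**The concern.** Whether a patient counts in a table for March to May 2020 depends on what that patient did with the tracker afterwards, or across the whole span of wear. Someone who wore it through the lockdown and then gave up monitoring, as the protocol allows, is removed from every month, including those with good data. If stopping or neglecting the tracker is related to activity, the period and month tables describe a selected group.

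The limit applies only to the tracker tables. The matching lockdown and by-month summaries for bleeds, EQ-5D-5L, pain and treatment adherence in SAP 4.4.2 name no such restriction. Nor is it needed for data quality within a day, because the 10-hour rule already screens every day analysed.

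At stake is the reading of the tables that the SAP provides to observe the impact of COVID-19 on activity. No sensitivity analysis is planned (SAP 4.4.3) and missing data are not imputed (SAP 4.7), so nothing specified for these tables would show the effect of the selection.

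**Working it through.** **1. The plan's own precision figure.** SAP 2.3 and 2.3.1 give a 95% half-width of at most 17% of the SD with over 80% probability at N = 150, and 20% with 80% probability at N = 107. The half-width met with 80% probability is w(n) = t(0.975, n-1) × sqrt[χ²(0.80, n-1) / (n(n-1))], in SD units.
- N = 150: w = 0.169, and P(half-width ≤ 0.17) = 0.831. This agrees with the SAP.
- N = 107: w = 0.202, which rounds to the stated 20%. At exactly 0.20 the probability is 0.75.

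**2. Who drops out of the tables.** SAP 4.4.4 gives the lockdown dates. Counting both ends:
- First: 31 + 30 + 4 = 65 days. Second: 19 + 30 + 31 = 80 days.
- Up to 179 consecutive valid days fails the 180-day rule. That is longer than either lockdown.
- Valid wear every day from 1 December 2019 to 4 May 2020: 31 + 31 + 29 + 31 + 30 + 4 = 156 days. The patient covers all 65 lockdown days and is excluded.
- 182 valid days over a 365-day span: 182/365 = 49.9%. Excluded.
- 90 valid days over a 180-day span: 50%. Kept, even if few of those days fall in a lockdown, and although 90/365 = 24.7% of a year.

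**3. Conflict between sections.** If Evaluable is under 50% of Enrolled, SAP 4.1.3 takes WHO adherence off Evaluable. SAP 4.4.2 still puts its lockdown and month tables on EVL only. Both cannot be followed.

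**4. Possible size.** The documents give no exclusion rate and no link between activity and wear, so both are assumed. Let q be the fraction excluded and r the correlation between the outcome and the tendency to stay Evaluable (bivariate normal). The shift in a period mean is r × φ(z_q)/(1-q) SD. The half-width uses n = 107(1-q), rounded.

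| q | n | φ(z_q)/(1-q) | shift, r = 0.1 | r = 0.2 | r = 0.3 | w(n) | shift / w(n) |
|---|---|---|---|---|---|---|---|
| 15% | 91 | 0.274 | 0.027 | 0.055 | 0.082 | 0.221 | 12-37% |
| 25% | 80 | 0.424 | 0.042 | 0.085 | 0.127 | 0.237 | 18-54% |
| 40% | 64 | 0.644 | 0.064 | 0.129 | 0.193 | 0.267 | 24-72% |
| 50% | 54 | 0.798 | 0.080 | 0.160 | 0.239 | 0.294 | 27-81% |

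The n here assumes that every Evaluable patient contributes to the period. Fewer will, since enrolment ran to 30 April 2021, so actual half-widths are wider and the ratios smaller.

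**The case against.** **Evaluable is the protocol's set.** This stands. Protocol 6.7 assigns these variables to Evaluable, and ITT is a SAP addition. A reader might infer a departure from the protocol; there is none. The question is only whether the SAP's own two-set rule reaches these tables.

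**SAP 4.1.3 may already imply an ITT version.** Possible, and the mock shells are in a separate attachment. But the specific lines name EVL alone, so the supportable statement is that no ITT version is specified, not that none will exist. Overall activity and WHO adherence are planned on both sets, which gives some indirect view of the selection.

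**The tables are supporting.** True. No study objective mentions COVID-19, and the primary summary overall and by age group is unaffected.

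**Two stronger readings are tempting.** One is that the tables show persistent wearers only. They do not: 90 valid days in a 180-day span is enough, and a patient who stops after that stays in. The other is that the tables overstate lockdown activity and understate the COVID-19 effect. Nothing in the documents links non-wear to activity, so the direction is open. SAP 4.4.4 also plans changes against the non-lockdown period, and a constant difference in level cancels in a within-patient change. The by-month tables show values only.

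**EVL steadies the composition.** Fair. In ITT month tables early stoppers appear and then leave, so month-to-month differences partly reflect who remains. That supports keeping EVL beside ITT, not omitting ITT.

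**Conclusion.** The point holds as a gap in specification. SAP 4.4.1 and 4.4.2 restrict the lockdown and month tables of daily activity, activity type and WHO adherence to a set defined by whole-study wear. Patients with valid data in the period are therefore dropped, and the restriction does not agree with SAP 4.1.3. The exclusions follow from the definitions and need no assumption.

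The consequence is uncertain. With 15-50% excluded and a correlation of 0.1-0.3, both assumed, a period mean moves by about 0.03-0.24 SD, or 12-81% of the half-width at the reduced n. Within that range the shift never exceeds the half-width. It concerns the level in a period; bias in the change between periods is not quantified, and the sign is unknown. This is a cheap improvement to supporting tables, not a threat to the primary result.

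**What to change.** In SAP 4.4.1, and in the activity-type and WHO-adherence parts of 4.4.2, specify the lockdown-period and by-month lines on the EVL and ITT populations. Let each ITT patient contribute to every period in which that patient has valid days, and report the number of contributing patients and valid days per period in both sets. Keep EVL as the protocol's set, with ITT as a companion; neither a change of lead population nor a new minimum number of days is needed. Define EVL in 4.1.2. State in 4.1.3 how the under-50% rule applies to the WHO-adherence period tables.

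The cost is SAP wording, a rerun of existing programs on ITT, and a few more tables, with no new data. The ITT by-month tables will change composition as early stoppers leave; the per-period counts make that visible.

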#### **4.4.2 Secondary and Exploratory Endpoints**

The endpoints assessed via the ePRO application that require to be evaluated at specific timepoint need to be “remapped” at each time point by deriving from the date the corresponding week/month starting from the baseline date. In case that more than one observation occurs within the same week/month, the mean among the two observations will be used.

**To document physical activity, particularly in terms of active minutes, by ages categories (12-17, 18-30 and 31-50 years), by type of physical activity and by intensity (as per fitness tracker default categorization)**

Data will be analyzed as for the primary endpoint described in Section 4.4.1 but they will be analyzed at activity level (instead of a daily level).

For example, if we consider “Bike”, the active minutes and METs will be derived as median of the active minutes (heart zone minutes, active zone minutes and MVPA minutes) for single activity (i.e. if Bike is reported twice, the active minutes for Bike will be derived as median of the values reported for each of two activities done).

Moreover, the activity rate will be derived as follow (in the example for “Bike”):

$$\text{Bike weekly rate} = \frac{\text{number of times that Bike is reported on the fitness tracker}}{\text{end of study date} - \text{baseline date} + 1} \times 7$$

For each type of activity, the statistics will be shown overall and by age groups (12-17, 18-30 and 31-50). The comparison among the age groups will be performed by means of a one-way ANOVA or, if assumptions of normality is not confirmed (by a visual inspection: histogram and qq-plot), by means of a Kruskal-Wallis test.

Daily physical activity will also be summarized:

- by start of any newly approved drug for haemophilia (see Section 4.4.4 for subgroup definition).
- by COVID-19 period on the EVL population (see Section 4.4.4 for subgroup definition).
- by month through the entire observational period on the EVL to observe the impact of COVID-19.

Data will be summarized at activity level considering data collected in each period above-mentioned.

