### **Bleeding and daily physical activity.**

The relationship between bleedings and physical activity (daily and by type) will be done as described in Section 4.4.1 but considering only data collected by the fitness tracker in the two days preceding the day in which the bleeding occurs.

For the relationship with daily physical activity, only data in the valid days will be considered. For each bleeding, the data collected in the two valid days before the bleeding will be summarized by the median. In case only one valid day is available, those values will be used to summarize the activity done before that bleeding.

All the activities recorded in the two days before the bleeding will be used regardless they occur in a valid day.

**To observe patients, on primary and secondary objectives, for additional 6 months if new therapies become commercially available for patients with Haemophilia A without inhibitors against FVIII, during the course of the study and if patient will start such treatments during the observation period.**

All the analysis proposed in sections 4.4.1 and 4.4.2 (except for the subgroup analyses) will be repeated by considering the start of any newly approved drug for haemophilia A during the study. See Section 4.4.4 for more details on this subgroup analysis.

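### The weekly activity rate divides tracker-recorded activities by all calendar days on study, so untracked days, above all those after a patient leaves monitoring, count as zero activity

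*SAP*

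**What the plan says.** SAP 4.4.2, under physical activity by type and intensity, defines a weekly rate for each activity type. The numerator is the "number of times that Bike is reported on the fitness tracker". The denominator is the number of days from baseline to end of study, both ends counted, and the ratio is multiplied by 7. Results for each type are shown overall and by three age groups, with ANOVA or Kruskal-Wallis. There are further summaries by start of a newly approved drug, COVID-19 period and month, but the formula has only a whole-study denominator.

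Other places bear on this formula:

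- Protocol 6.5.1: "Patients may elect to withdraw from the physical activity monitoring but continue participation in the remainder of the study".
- SAP 2.2: "Only data from days in which the fitness tracker was worn for at least 10 hours will be included in the statistical analysis". In 4.4.1 the co-primary medians are "calculated by using all the valid days collected during the observational period for each subject".
- SAP 4.4.2, on bleeding and activity type: "All the activities recorded in the two days before the bleeding will be used regardless they occur in a valid day".
- SAP 4.1.2: an Evaluable patient needs 180 days between first and last valid day, and "a compliance to the use of the fitness tracker of at least 50% in the period defined by the extent of exposure". The ITT population (4.1.3) has no wear minimum, and all objectives are evaluated there too.
- SAP 4.3.2: compliance (valid days over the same calendar denominator) is summarised by age group.

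**The concern.** Numerator and denominator cover different time. An activity can be counted only while the tracker is worn and transmitting; the denominator runs to the end of follow-up regardless. Every day that cannot be recorded is therefore entered as a day without the activity. Once a patient leaves monitoring and stays on study, the denominator keeps growing and the numerator cannot.

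This rate is the SAP's only measure of how often each type of activity is done. Its level mixes behaviour with tracker use, so a reader could take poor recording for low activity. If tracker use also differs by age, part of an age difference in the rate could come from recording alone.

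**Working it through.** The plan states no numerical weekly rate, so there is no figure to reproduce. The check applies the formula to assumed cases. End of study is read as the patient's own date, as in the bleeding-rate formula of SAP 2.2.1.

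**Inputs.** From the documents: 12 months (365 days), the 180-day exposure minimum, the 50% compliance minimum, 107 patients enrolled. Assumed: a constant true rate of 3 activities per week.

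**One patient, tracker stopped at day 180, full recording until then.** Recorded activities: 3 × 180/7 = 77.1. SAP rate: 77.1/365 × 7 = 3 × 180/365 = 1.48, or 51% too low. This is an upper limit whichever activities are counted, because none can be recorded after day 180. Exposure is 180 days at 100% compliance, so the patient is Evaluable. Over the tracked period the rate is 77.1/180 × 7 = 3.00.

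**A group in which a share p does this and the rest are fully recorded.** Mean = 3 × (1 − p + p × 180/365):

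| p | Group mean | Change |
|---|---|---|
| 10% | 2.85 | −5% |
| 20% | 2.70 | −10% |
| 30% | 2.54 | −15% |

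**Gaps in wear while the tracker is still in use.** If only activities on valid days count, and wear is unrelated to activity, the SAP rate equals the true rate times the 4.3.2 compliance: 3 × 0.8 = 2.4 at 80% and 3 × 0.5 = 1.5 at 50%. If all recorded activities count, the loss is smaller, because activities recorded on short-wear days are kept; days with no wear still score zero.

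**Age comparison.** Simulation with identical behaviour in all age groups: 36/36/35 patients, 365 days, gamma patient rates, Poisson counts, 3,000 runs per scenario, nominal 5%. Mean 3 per week, except that with non-participants the others average 1 per week. CV is the between-patient coefficient of variation; q is the share of activities on non-valid days that is still recorded. Rejection by ANOVA / Kruskal-Wallis:

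| Difference by age | CV 0.4 | CV 0.8 | CV 1.5 | 50% non-participants |
|---|---|---|---|---|
| 10/20/30% leave monitoring at day 180, all earlier sessions recorded | 14/15% | 8/9% | 5/6% | 6/5% |
| Compliance 50/65/80%, q = 0 | 99/99% | 55/49% | 16/12% | 17/7% |
| Compliance 50/65/80%, q = 50% | 36/33% | 11/10% | 6/6% | 7/5% |
| Compliance 60/65/70%, q = 50% | 7/6% | 6/6% | 5/5% | 4/5% |

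The distortion runs from none to large, depending on quantities the documents do not give.

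**Does a valid-day denominator solve it?** Only if wear is unrelated to activity. Take a daily session probability of 3/7, with 90% of session days and 70% of other days valid. Valid share of days: 0.9 × 3/7 + 0.7 × 4/7 = 0.786. Valid-day rate: 7 × (0.9 × 3/7)/0.786 = 3.44. Calendar rate with the same numerator: 0.9 × 3 = 2.70. Against a true 3, the calendar rate is closer. In a simulation with identical behaviour (CV 0.4), 90% of session days valid in every group, and 50/70/90% of other days valid by age, the valid-day rate rejected in 81% of runs by ANOVA and 84 to 85% by Kruskal-Wallis. The calendar rate stayed at 4 to 5%.

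**The case against.** The strongest defence is that the formula is a defined quantity: recorded sessions per week on study. The SAP uses the same per-patient calendar time for missed days and hospitalisation, and compliance by age has the identical denominator, so a reader can see the tracked share. That holds as far as it goes. But missed days and hospitalisation are patient-reported and do not depend on the tracker, the rate is not labelled as recorded sessions, and the compliance table does not yield a corrected rate. Where the SAP wants missing data to count as negative, as for treatment adherence, it says so; here it does not.

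A reader might infer that the SAP breaks its own valid-day rule. The documents do not support that. SAP 2.2 limits analysis to valid days, but 4.4.2 treats these data at activity level, and the bleeding analysis uses activities on non-valid days. A recorded session may be complete even when the tracker was worn for under 10 hours. The basis is unsettled, not violated.

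A reader might also infer that a valid-day rate is simply the right one. Under preferential wear it can be further from the truth than the SAP's rate and can create false age differences, so this part of the objection stands and shapes the fix.

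Finally, the mock shells and the wearing-time report are attachments that were not available. That nothing corrects the denominator is a statement about the protocol and SAP text only.

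**Conclusion.** The concern holds for the level of the rate. It is understated for any patient who does the activity on untracked days, most clearly after leaving monitoring: at most 1.48 against an assumed true 3 per week for a stop at day 180 of 365. The proportional loss does not depend on the assumed 3; it does depend on activity continuing at the same rate after the tracker stops. Wear gaps before that add a further loss whose size turns on the unstated numerator rule.

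Three stronger readings are not supported:

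- That every reported rate is too low. For an activity the patient does not do on untracked days, nothing is understated, and many patients may never do a given type.
- That Evaluable patients should be expected at about a quarter of their true rate. The value 3 × 90/365 = 0.74 needs the minimum of 90 valid days (50% of 180) and a numerator limited to valid days.
- That the age comparison is invalid. The 99% rejection needs that same numerator, a steep compliance gradient and little variation between patients. No wear by age is given, and the effect may be negligible. That the rate itself is tested by age is the likely reading of 4.4.2, not an explicit statement.

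The endpoint is secondary, the tests are exploratory, and the co-primary and per-activity medians are unaffected. The change is worth making because the level is wrong by construction and correcting the denominator is simple.

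**What to change.** 1. Count activities and days over the same tracked time. Replace the denominator with the patient's tracked period (first to last day with tracker data, or the exposure days of SAP 4.3.1), and cut it to the relevant period or month for those summaries. Days after the tracker stops then no longer score as zero, and this step does not rely on wear being unrelated to activity.
2. State whether activities on days under 10 hours' wear are counted, and whether the rate is part of the age-group test.
3. Beside this rate, show a valid-day rate (activities on valid days / valid days × 7, with a pre-stated minimum number of valid days) and the calendar-time rate, next to the compliance by age already planned in 4.3.2.
4. Footnote the limits. Gaps within the tracked period still lower the tracked-period rate. The valid-day rate assumes wear is unrelated to activity; otherwise it can overstate the level (3.44 against 3 in the example) and create false age differences.

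The cost is one formula line, one or two extra table rows and the footnotes. No new data are needed, since exposure and valid days are already derived. The drawback is instability in patients with little tracked time, chiefly in ITT. With Poisson counts at 3 per week, the standard error of one patient's rate over V recorded days is √(21/V): 2.65 for 3 days, 0.84 for 30 and 0.48 for 90. Hence the stated minimum for the valid-day rate.
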